In each dose cohort, 8 subjects will be randomly assigned to each of the 4 brentuximab vedotin doses and 2 subjects to placebo (total of 8 placebo subjects overall). Initiation of enrollment at the next dose level will only commence after the final subject of each cohort has been evaluated at the Day 43 visit, and upon endorsement of the Safety Monitoring Committee (SMC) following review of the safety data. Depending on the findings, the SMC may recommend additional enrollment of subjects at specific dose levels to better characterize the safety of a particular dose, or may recommend different dose regimens based on the emerging safety data. When available from each full cohort, the SMC will review all Day 85 safety data and may recommend that an already enrolled succeeding dose cohort be discontinued, or its treatment regimen truncated. Doses are not to exceed 1.8 mg/kg IV every 3 weeks or equivalent.				
Assessments for safety (including progressive multifocal leukoencephalopathy [PML] monitoring), efficacy, PK, and PD will be performed throughout the study. Following the last dose of study drug, there will be a 6-week observation period and a final follow-up visit 3 weeks later.				
Number of Subjects:				
40 (10 per dosing cohort); up to 20 additional subjects may be enrolled via additional SMC-recommended cohorts for a total of up to 60 subjects.				

Name of Sponsor/Company: Seattle Genetics, Inc.	
Name of Finished Product: Brentuximab vedotin	
Name of Active Ingredient: Brentuximab vedotin	
Diagnosis and Main Criteria for Inclusion:	
Subjects must have a documented diagnosis of SLE for at least 6 months prior to screening according to both of the following:	

• fulfills at least 4 of 11 of the 1997 Update of the 1982 American College of Rheumatology Revised Criteria for Classification of SLE; and

• has a history of positive antinuclear antibody (<math>\geq 1:80</math>) or anti-double-stranded deoxyribonucleic acid (<math>\geq 30</math> IU/mL) test prior to screening.

	
Subjects must demonstrate active SLE as indicated by SLE Disease Activity Index (SLEDAI) score $\geq 4$ points at screening and at baseline.	
The subject must have failed at least one of the following treatments for SLE after a trial of at least 3 months:	

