## 4.0 INVESTIGATIONAL PLAN

### 4.1 Summary of Study Design

This is a multicenter, randomized, placebo-controlled, double-blind, multiple-ascending-dose study to evaluate the safety and tolerability of brentuximab vedotin in subjects with active SLE. Approximately 40 subjects in 4 dosing cohorts (10 subjects per cohort) are planned for study participation at approximately 20 study sites in the US. Subjects who meet inclusion and exclusion criteria will be randomly assigned in a 4:1 ratio within each dosing cohort to receive IV brentuximab vedotin or placebo every 3 weeks (Days 1, 22, 43, and 64) for a total of 4 doses. The following doses are planned for each ascending dose cohort:

[figure not shown]
- 0.3 mg/kg IV every 3 weeks for 4 doses;
- 0.6 mg/kg IV every 3 weeks for 4 doses;
- 1.2 mg/kg IV every 3 weeks for 4 doses; and
- 1.8 mg/kg IV every 3 weeks for 4 doses.

There will be a total of 10 subjects in each dose cohort with 8 subjects randomly assigned to each of the 4 brentuximab vedotin doses and 2 subjects to placebo (for a total of 8 placebo subjects overall). Initiation of enrollment at the next dose level will only commence after the final subject of each cohort has been evaluated at the Day 43 visit, and upon endorsement of the SMC following review of the safety data. Depending on the findings, the SMC may recommend additional enrollment of subjects at specific dose levels to better characterize the safety of a particular dose, or may recommend different dose regimens based on the emerging safety data. When available from each full cohort, the SMC will review all Day 85 safety data and may recommend that an already enrolled succeeding dose cohort be discontinued, or its treatment regimen truncated. Doses are not to exceed 1.8 mg/kg IV every 3 weeks or equivalent. Up to 20 subjects total may be enrolled via additional SMC-recommended cohorts for a total of up to 60 subjects.

Assessments for safety (including PML monitoring, see Section 6.3.3), efficacy, PK, and PD will be performed at the times indicated in the schedule of events (see [Table 3](#)). Following the last dose of study drug, there will be a 6-week observation period (through Day 106) and a follow-up visit will take place at Day 127.

A flowchart of the study design is presented in [Figure 1](#).

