### **4.4 Selection of Study Population**

#### **4.4.1 Inclusion Criteria**

Subjects may be entered in the study only if they meet all of the following criteria:

1. Subject is able to provide written, informed consent.

2. Subject is an adult, aged  $\geq 18$  years.
3. Women of childbearing potential or male subjects with a WOCBP partner, will use 2 forms of highly-effective contraception method during the study through 6 months following the last dose of study drug. Women of childbearing potential includes any female who has experienced menarche and who has not undergone successful surgical sterilization (hysterectomy, bilateral tubal ligation, or bilateral oophorectomy) or is not postmenopausal. Postmenopausal is defined as amenorrhea  $\geq 12$  consecutive months without another cause, or documented follicle-stimulating hormone level  $> 35$  mIU/mL for women with irregular menstrual periods and on hormone replacement therapy (HRT). Acceptable forms of effective contraception include: established use of oral, injected, or implanted hormonal methods of contraception; placement of an intrauterine device or intrauterine system; barrier methods of contraception (condom or occlusive cap) with spermicidal foam/gel/film/cream/suppository; male sterilization; and true abstinence. Women of childbearing potential taking concomitant mycophenolate and oral contraceptives must use a barrier method of contraception along with their oral contraceptives.
4. If subject is a WOCBP, a serum pregnancy test result at screening and urine pregnancy test result at baseline must be negative.
5. Subjects must have a documented diagnosis of SLE for at least 6 months prior to screening according to both of the following:
  - a. fulfills at least 4 of 11 of the 1997 Update of the 1982 American College of Rheumatology (ACR) Revised Criteria for Classification of SLE; and
  - b. has a history of positive ANA ( $\geq 1:80$ ) or anti-dsDNA ( $\geq 30$  IU/mL) test prior to screening.
6. Subjects must have a positive ANA ( $\geq 1:80$ ) or anti-dsDNA ( $\geq 30$  IU/mL) test at screening (a single rescreening of previously positive subjects who were negative at screening will be allowed).
7. Subjects must demonstrate active SLE as indicated by a SLEDAI score  $\geq 4$  points at screening and at baseline.

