### **5.3 Method of Assigning Subjects to Treatment Group**

Once the subject meets inclusion and exclusion criteria and has provided written informed consent, the study site will request the study medication assignment using the Interactive Web Response System (IWRS).

A total of 10 subjects in each dose cohort will be randomly assigned in a 4:1 ratio, resulting in 8 subjects assigned to each of the 4 brentuximab vedotin dose cohorts and a total of 8 subjects assigned to placebo (2 per cohort).

To randomly assign a subject to treatment, the study site will use the internet to access the IWRS. Subjects will be assigned their 6-digit subject number, starting with a 3-digit site number followed by a hyphen and a 3-digit sequential number (eg, 101-001). The IWRS will provide the study drug kit number(s) of the blinded study drug to be dispensed.

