7. STATISTICAL CONSIDERATIONS

7.1. ADJUSTMENT FOR COVARIATES

The baseline value for a dependent variable will be used as a continuous covariate in statistical models when available.

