15.2.1.1. DERIVATION

The SRI definition of response includes meeting all of the following criteria:

- Reduction from baseline in SLEDAI of at least 4 points;
- no new British Isles Lupus Assessment Group (BILAG) A organ domain scores, relative to baseline
- no more than 1 new BILAG B score, relative to baseline;
- no worsening (increase of < 10% of scale length) in PhGA, relative to baseline.

Assessment for response will be made using data only for the visit of interest and baseline, without regard for changes at prior on-treatment visits.

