15.2.1.2. ANALYSIS

The following analyses will be performed for all study days with Day 85 specified as the secondary endpoint, and all other visits falling under exploratory analyses.

The percentage of subjects demonstrating SRI Response will be presented by treatment with 95% CI using Wilson's score method (SAS PROC FREQ syntax: table response/binomial (wilson)). Comparisons between each active treatment group and placebo will be performed using Fisher's exact test (two-sided). The ratio of percentages (relative risk) for active to placebo will be presented for each dose level with corresponding 95% CI, based on the score method [Farrington] (SAS PROC FREQ syntax: table trta*response / relrisk(method=score equal)). Percentages with Wilson 95% CI will be plotted versus study day per treatment, with all treatments overlain.

Logistic regression of the log odds of SRI response on log2 dose level (mg/kg) will be performed. Placebo subjects will be treated as a having dose of 0 mg/kg. Based on this model, the estimate of the slope and odds ratio (OR) for a doubling of dose will be presented with 95% CI (based on the profile likelihood) and two-sided p-value (Wald test).

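### The SRI logistic dose model leaves out baseline SLEDAI, so a baseline difference between dose groups can distort the slope; adjusting is a modest, optional improvement

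*SAP*

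**What the plan says.** SAP 15.2.1.2 sets out three analyses of SRI response: Fisher's exact test of each dose against placebo, relative risks, and a dose-response model. For the model it says "Logistic regression of the log odds of SRI response on log2 dose level (mg/kg) will be performed", followed by "Placebo subjects will be treated as a having dose of 0 mg/kg". No covariate is named for any of the three.

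SRI is built on a change score. SAP 15.2.1.1 requires "Reduction from baseline in SLEDAI of at least 4 points", together with BILAG and PhGA conditions. The Protocol synopsis admits subjects with "SLE Disease Activity Index (SLEDAI) score $\geq 4$ points at screening and at baseline", and inclusion criterion 7 in Protocol 4.4.1 repeats this.

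SAP 7.1 has a general rule: "The baseline value for a dependent variable will be used as a continuous covariate in statistical models when available". The continuous SLEDAI-2K change is adjusted for baseline, because SAP 15.3.4.2 takes over the covariance model of SAP 15.3.3.2.

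On design, Protocol 5.3 says "A total of 10 subjects in each dose cohort will be randomly assigned in a 4:1 ratio", and neither document describes a stratification factor. Protocol 4.1 makes the cohorts sequential: "Initiation of enrollment at the next dose level will only commence after the final subject of each cohort has been evaluated at the Day 43". Placebo subjects are pooled across cohorts (Protocol 8.2, SAP 6.1).

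**The concern.** Baseline SLEDAI limits who can meet the SLEDAI component of SRI, and it is already collected on Day 1. The rule in SAP 7.1 works through the baseline value of the dependent variable. SRI is a yes/no change outcome and has none, so the rule passes it by. The continuous SLEDAI change is therefore adjusted for baseline, while the responder endpoint built on that change is not.

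Two things are at stake. One is precision in a study with 8 subjects per dose. The other is the reading of the slope in the trial actually run. Subjects are randomised to active or placebo within a cohort, but not between dose levels. Dose groups may therefore differ in baseline severity by chance, or because the kind of subject enrolled changes as the cohorts fill. The second kind of difference is not covered by the confidence interval. Protocol 8.1 says the study is to inform the design of a larger efficacy study, so a misleading dose slope would have consequences.

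**Working it through.** **Inputs from the documents.** Allocation is 4 × 8 active + 4 × 2 placebo = 40, which agrees with the planned total. Doses are 0.3, 0.6, 1.2 and 1.8 mg/kg. Tests are two-sided at a nominal 5%. Sample size rests on clinical judgment (Protocol 8.1, SAP 3.1.1), so there is no power figure to reproduce.

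**Assumptions, not in the documents.** Baseline SLEDAI is at least 4 with mean about 9 and SD 3 or 4. Response is about 40%. The odds ratio for response per baseline point is 1.0, 1.1, 1.2 or 1.4.

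**1. Floor.** Entry at 4 less the required fall of 4 leaves 0, the lowest possible score (SAP 15.3.4).

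**2. Chance imbalance between two arms of 8.** The SD of the difference in means is SD × √(2/8) = SD/2.
- SD 3: 1.5 points; P(|difference| ≥ 2) = 2 × P(Z > 2/1.5) = 18%.
- SD 4: 2.0 points; P(|difference| ≥ 2) = 2 × P(Z > 2/2.0) = 32%.

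**3. Trials with no dose effect.** Logistic regression on log2 dose, 32 active subjects (log2 of 0 cannot be computed), Wald test, 4,000 trials per row. The last two columns cover the 10% of trials in which baseline rises most steeply with dose, without adjustment.

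| OR per point | SD | Rejects, unadjusted | Rejects, adjusted | Median OR per doubling, worst 10% | Rejects, worst 10% |
|---|---|---|---|---|---|
| 1.0 | 3 | 4.3% | 4.1% | 1.03 | 4.2% |
| 1.0 | 4 | 4.3% | 4.5% | 1.00 | 4.3% |
| 1.1 | 3 | 4.5% | 4.6% | 1.11 | 5.8% |
| 1.1 | 4 | 4.0% | 4.0% | 1.11 | 4.8% |
| 1.2 | 3 | 3.8% | 4.1% | 1.11 | 5.0% |
| 1.2 | 4 | 4.9% | 4.4% | 1.27 | 7.0% |
| 1.4 | 3 | 4.9% | 4.3% | 1.27 | 6.8% |
| 1.4 | 4 | 4.4% | 3.5% | 1.42 | 9.8% |

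Over all trials the unadjusted level holds, and the median slope is about 0. With five groups of 8 and a placeholder placebo code, a likelihood-ratio test rejected in 6.1% and 6.2% of null trials without and with baseline. That small excess is therefore not caused by leaving baseline out.

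**4. Drift across cohorts.** Suppose mean baseline rises by 2 points from the lowest to the highest cohort in equal steps (0, 0.67, 1.33, 2).
- The log2 doses are −1.737, −0.737, 0.263 and 0.848, with mean −0.341.
- The slope of baseline on log2 dose is 2.918/3.884 = 0.751 points per doubling.
- To a first approximation, the spurious odds ratio per doubling is (OR per point)^0.751: 1.07, 1.15 and 1.29 for 1.1, 1.2 and 1.4 per point.
- Simulation (SD 4) gave 1.08, 1.13 and 1.20. Rejection was 4.1%, 5.3% and 6.1% unadjusted, and 4.3%, 4.0% and 3.6% adjusted.

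**5. Power with and without baseline.**

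| Set-up | Unadjusted | Adjusted |
|---|---|---|
| 32 active, OR 2 per doubling, 1.1 per point | 37% | 38% |
| Same, 1.2 per point | 33% | 34% |
| Same, 1.4 per point | 26% | 28% |
| Five groups of 8, proportional reduction, noise SD 3 | 33.9% | 36.1% |
| Same, noise SD 2 | 55.5% | 62.3% |
| Five groups of 8, constant-point reduction, first setting | 39.5% | 38.7% |
| Same, second setting | 71.0% | 70.8% |

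The differences run from −0.8 to 6.8 points. Other proportional-reduction settings gave gains of 2 to 6 (35% to 37%, 46% to 50%, 60% to 66%, 74% to 80%). About 0 to 6 is a fair summary, not a bound.

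**6. Placebo coding.** log2(0) is undefined. As written, the model either drops the 8 placebo subjects or cannot be fitted. The five-group figures rest on a placeholder code, so they describe a completed version of the model.

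**The case against.** A reader might infer that chance imbalance is simply read as a dose effect and inflates false positives. The documents do not support that, and step 3 contradicts it. Chance imbalance is ordinary sampling error, already carried by the interval and the p-value. This part of the case against the concern stands in full.

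It also stands that the documents nowhere say how strongly baseline SLEDAI predicts SRI. Calling it the strongest available predictor would be an assertion. With a constant-point reduction the power gain vanishes. The BILAG and PhGA conditions of SRI would dilute any effect seen on the SLEDAI fall alone.

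Two further extensions are tempting and fail. BICLA copies the SRI analysis, but SAP 15.3.2.1 asks only that SLEDAI-2K not worsen and defines improvement by BILAG grade, so the floor argument does not apply. Nor would adjusting the logistic model protect the comparison that Protocol 8.5.2 names: the Fisher tests, and the SAP's relative risks, stay unadjusted.

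Finally, readers already have a baseline-adjusted analysis of the SLEDAI-2K score. Testing is nominal (Protocol 8.2) and the study is hypothesis generating (SAP 7.4). These points lower the priority. They do not remove the gap in the model or the exposure to drift between sequential cohorts.

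**Conclusion.** The point holds in a limited form. The SRI dose model has log2 dose as its only term, and SAP 7.1 does not bring in baseline SLEDAI. On average the unadjusted test is valid under chance imbalance. In the particular trial, an unlucky draw can move a null odds ratio per doubling to between 1.11 and 1.42 if baseline is prognostic, and a 2-point drift across cohorts moves it to between 1.08 and 1.20. Adjustment largely removes the drift effect on rejection and gains about 0 to 6 points of power. All of these sizes rest on assumed baseline distributions and an assumed link to response. If baseline does not predict SRI, the distortion and the gain are both about nil. The documents contain no evidence that drift has occurred; the design merely allows it. Severity: optional.

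**What to change.** In SAP 15.2.1.2, add baseline total SLEDAI as a continuous covariate to the SRI logistic model, using the SLEDAI version that scores the SRI component. Make the same change for SLEDAI clinical response in SAP 15.3.4.2. State that the term does not carry over to BICLA or to the other endpoints that replicate the SRI analysis: BILAG response, ACR response, the flare endpoints, active renal disease and corticosteroid use. Leave the Fisher tests and relative risks as they are. A table of baseline SLEDAI by dose group would let readers see any imbalance or drift.

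In the same edit, define how placebo enters a model on the log2 scale. The model cannot include placebo subjects until this is settled.

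The cost is a few sentences before unblinding, with no new data. The odds ratio becomes conditional on baseline, so it is no longer on the same footing as the unadjusted relative risks, and one more parameter is estimated from 40 subjects.

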5.4. PHARMACOKINETIC ANALYSIS SET

The PK analysis set (PKAS) includes all randomized subjects who have received at least 1 dose of brentuximab vedotin, have a post-baseline PK measurement. The PKAS will be analyzed according to the treatment administered.

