15.3.1.2. ANALYSIS

BILAG domain scores will be tabulated by treatment group at each visit, plus categories for grade B or worse and grade C grade or better. Shifts from baseline among the grades will be tabulated similarly. Individual grades for each domain will be graphed over time, treating grade as ordinal, with one plot per subject.

The analysis for BILAG clinical response (full and partial) will replicate that performed for SRI.

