15.3.2.2. ANALYSIS

The analysis for BICLA response will replicate that performed for SRI.

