15.3.4.2. ANALYSIS

The analyses for SLEDAI-2K scores will replicate those performed for CLASI.

The analysis for SLEDAI clinical response will replicate those performed for SRI.

Boxplots profiles of SLEDAI-2K through time (study day) for each dose level. Stacked bar graphs will be generated for each subject with all visits included, with stacks comprised of the scoring domains, and dose levels comprising separate pages.

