16.3. ANALYSES

A listing of PK blood sample collection times as well as derived sampling time deviations will be provided.

Plasma concentrations will be summarized using descriptive statistics for each treatment group/dose level. Concentrations that are below the limit of quantitation (BLQ) will be treated as zero for the computation of descriptive statistics. Figures of arithmetic mean concentration-time data \pm SD will be presented for each treatment on linear and semi-logarithmic scales. The incidence of antitherapeutic antibodies will be tabulated.

A subject listing of all concentration-time data for each treatment will be presented. Individual subject concentration-time data will be graphically presented on linear and semi-logarithmic scales.

Plasma parameters will be summarized using descriptive statistics for each treatment group/dose level. Dose proportionality will be assessed using least-squares regression of the log-transform PK parameters on log dose. Slope and intercept estimates will be presented with 90% CI. AUC and Cmax parameters will be plotted vs dose on the log-log scale, with the regression lines overlain.

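### The SRI dose-response model takes log2 of dose but gives placebo a dose of 0 mg/kg, so it cannot be fitted as written for the 8 planned placebo subjects

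*SAP*

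**What the plan says.** SAP 15.2.1.2 sets out the analysis of SRI response. After the Wilson intervals, Fisher's exact test and relative risks, it adds a dose-response model: "Logistic regression of the log odds of SRI response on log2 dose level (mg/kg) will be performed". The next sentence reads "Placebo subjects will be treated as a having dose of 0 mg/kg". From this model the SAP will report the "estimate of the slope and odds ratio (OR) for a doubling of dose", with a profile-likelihood 95% CI and a Wald p-value.

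Protocol 4.1 plans 8 placebo subjects, 2 in each of four cohorts of 10, and SAP 6.1 pools them into one group. Day 85 is the secondary endpoint; the same analysis is run at the other visits as exploratory.

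Nine later sections reuse the analysis by reference, for example "The analysis for BILAG clinical response (full and partial) will replicate that performed for SRI" (15.3.1.2), "The analysis for BICLA response will replicate that performed for SRI" (15.3.2.2) and "The analysis for SLEDAI clinical response will replicate those performed for SRI" (15.3.4.2). The other six are 15.3.7.2 (ACR), 15.3.8.2 (SELENA flares), 15.3.9.2 (BILAG flares), 15.3.10.2 (renal flares), 15.3.11.2 (active renal disease) and 15.3.12.2 (corticosteroid use).

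**The concern.** The two sentences cannot both be carried out. The covariate is a logarithm of dose, and placebo is given the one dose that has no logarithm. The text shows that placebo is meant to be in the model but not where it sits on the axis.

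This model is the only SRI analysis that uses the ordering of the doses, in an ascending-dose study meant to inform a larger Phase 2 trial. If no rule is written down, whether placebo counts, and at what value, is settled in programming, possibly after the treatment codes are open. If the software sets the value to missing, the 8 placebo subjects leave the fit and an active-only slope appears under a description that says placebo is included.

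**Working it through.** **Inputs.** Doses 0.3, 0.6, 1.2 and 1.8 mg/kg, with 8 active and 2 placebo subjects per cohort (Protocol 4.1). Model and placebo dose are from SAP 15.2.1.2.

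**Counts.** Placebo 4 × 2 = 8; active 4 × 8 = 32; total 40, as planned. 8/40 = 20%.

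**Covariate.** log2 of 0.3, 0.6, 1.2 and 1.8 is −1.74, −0.74, 0.26 and 0.85. log2(0) is minus infinity. Only 32 subjects have a usable value.

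**Can the text be read another way?**
- *Placebo drops out as missing.* This contradicts the sentence that gives placebo a dose.
- *The log2 term itself is 0.* The text gives the unit mg/kg, so it means a dose. Since 2^0 = 1, this reading also places placebo at 1 mg/kg, between the second and third active doses.
- *A constant is added before taking logs.* No constant is given, and the slope would no longer be per doubling of dose.

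**Does the SAP's other log-dose regression settle it?** No. SAP 16.3 says "Dose proportionality will be assessed using least-squares regression of the log-transform PK parameters on log dose", but the PK analysis set "includes all randomized subjects who have received at least 1 dose of brentuximab vedotin", so zero never arises there.

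**Effect of the choice.** The documents contain no response data, so responder counts are assumed, with 8 evaluable subjects per group. The model is logit(p) = a + b·x; the table gives exp(b), the profile-likelihood 95% CI and the Wald p. Responders 1, 3, 4, 5, 5 (placebo to 1.8 mg/kg):

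| Placebo coding | OR | 95% CI | p |
|---|---|---|---|
| Dropped (n=32) | 1.52 per doubling | 0.75–3.27 | 0.257 |
| 0.15 mg/kg | 1.84 per doubling | 1.10–3.33 | 0.027 |
| 0.001 mg/kg | 1.27 per doubling | 1.04–1.71 | 0.046 |
| log2 term = 0 | 1.35 per doubling | 0.67–2.86 | 0.415 |
| Linear mg/kg, placebo 0 | 1.92 per 0.6 mg/kg | 1.05–3.80 | 0.043 |
| Ordinal 0–4 | 1.73 per step | 1.08–2.96 | 0.031 |

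A placebo indicator plus log2(dose/0.3) gives a doubling OR of 1.52 (p=0.257), the same as dropping placebo, and an OR of 4.43 (p=0.230) for 0.3 mg/kg against placebo.

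Including placebo does not always strengthen the slope. With 4, 3, 4, 5, 5, dropping placebo gives 1.52 (p=0.257), 0.15 mg/kg gives 1.24 (p=0.375) and 0.001 mg/kg gives 1.03 (p=0.68). With 1, 5, 5, 5, 5, the OR is 0.87 (log2 term 0), 1.00 (dropped) or 1.61 (0.15 mg/kg), so the sign of the slope can depend on the coding.

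**How often two codings disagree.** 50,000 simulated trials per pattern, 8 per group, two-sided 5% Wald test. Share of trials in which dropping placebo and setting it to 0.15 mg/kg fall on opposite sides of p=0.05:

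| Assumed rates, placebo/0.3/0.6/1.2/1.8 (%) | Disagree |
|---|---|
| 20/20/30/50/60 | 26.7% |
| 30/30/40/50/60 | 21.3% |
| 30/35/40/50/55 | 16.6% |
| 20/30/40/50/60 | 28.8% |
| 40/30/40/50/60 | 18.4% |
| 30/20/30/50/60 | 25.7% |
| 30 in every group | 5.5% |

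Simulation error is at most 0.22 percentage points.

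**Is this a power problem?** Not in general. Power with placebo dropped, against linear/ordinal, is 42% vs 55%/54% for the first pattern, but 22% vs 20%/17% for 40/30/40/50/60 and 42% vs 41%/37% for 30/20/30/50/60.

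**The case against.** The strongest reply concerns weight. Protocol 8.5.2 plans exact confidence intervals and Fisher's test for SRI; the logistic model appears only in the SAP. There is no primary efficacy endpoint, the primary objective is safety, p-values are nominal, and SAP 7.4 calls the study hypothesis generating. No decision rule depends on this slope, and all nine replications are exploratory. All of this stands, and it keeps the point from ranking higher.

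It can also be said that the disagreement rates compare different questions: an active-only slope in 32 subjects against a trend in 40 that includes placebo. The 0.15 mg/kg value is not in the documents, and the first responder pattern happens to straddle 0.05. That is fair. The figures show that an unstated choice can matter; they do not predict how often this trial's result would change. In the 4, 3, 4, 5, 5 example no coding comes near significance.

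Two of the acceptable repairs also reproduce the dropped-placebo slope, so for the OR per doubling the harm is largely one of labelling. This is true if the active-only model is what the SAP wants, but at present the SAP says the opposite.

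Finally, the output templates mentioned in SAP 8 were not available and might hold a rule. Even so, the model text in the SAP would still need correcting.

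**Conclusion.** The concern holds. As written, the model has no covariate value for 8 of the 40 planned subjects (more placebo subjects are possible if cohorts are added), and neither document says what to do. This is a stated rule that cannot be executed, not a preference between methods. On assumed counts, the choice of coding moves the OR per doubling from 1.27 to 1.84 and the p-value from 0.027 to 0.415. Two plausible codings disagree at the 5% level in about 17% to 29% of simulated trials with a dose effect, and in 5.5% with none. These sizes rest on invented response rates and complete data in groups of 8; the undefined logarithm does not. The point should be fixed before unblinding, but it touches only the dose-response model in SAP 15.2.1.2 and its nine replications. Fisher's test, the Wilson intervals, the relative risks and the ANCOVA analyses do not depend on it.

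**What to change.** Before unblinding, replace the two sentences in SAP 15.2.1.2 with one of the following.

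1. A dose scale that exists at placebo: linear mg/kg with placebo at 0 (OR per 0.6 mg/kg), or an ordinal score 0 to 4. The OR for a doubling of dose is then dropped. This tests a trend that includes placebo.
2. A placebo-versus-active indicator plus log2(dose/0.3), with that term set to 0 for placebo. Report both coefficients and state that the slope is the active-only slope.
3. An active-only model, with the 0 mg/kg sentence deleted.

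The power figures do not favour one scale consistently, so the choice should follow from whether the question is a trend from placebo upward or a slope among active doses. Apply the same coding to the nine replicating sections. The cost is one or two sentences and a few lines of code, with no new data.
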